APPENDIX 2. PARTIAL DATE CONVENTIONS

Imputed dates will NOT be presented in the listings.

Algorithm for Treatment Emergence of Adverse Events:

START DATE	STOP DATE	ACTION
Known	Known	If start date < study med start date, then not TEAE If start date >= study med start date and <=study med end date + 30, then TEAE
	Partial	If start date < study med start date, then not TEAE If start date >= study med start date and <=study med end date + 30, then TEAE
	Missing	If start date < study med start date, then not TEAE If start date >= study med start date and <=study med end date + 30, then TEAE
Partial, but known components show that it cannot be on or after study med start date	Known	Not TEAE
	Partial	Not TEAE
	Missing	Not TEAE
Partial, could be on or after study med start date	Known	If stop date < study med start date, then not TEAE If stop date >= study med start date and <=study med end date + 30, then TEAE
	Partial	Impute stop date as latest possible date (i.e. last day of month if day unknown or 31st December if day and month are unknown), then: If stop date < study med start date, then not TEAE If stop date >= study med start date and <=study med end date + 30, then TEAE
	Missing	Assumed TEAE
Missing	Known	If stop date < study med start date, then not TEAE If stop date >= study med start date and <=study med end date + 30, then TEAE
	Partial	Impute stop date as latest possible date (i.e. last day of month if day unknown or 31st December if day and month are unknown), then: If stop date < study med start date and <=study med end date + 30, then not TEAE

Statistical Analysis Plan

START DATE	STOP DATE	ACTION
		If stop date >= study med start date and <=study med end date + 30, then TEAE
	Missing	Assumed TEAE

Algorithm for Prior / Concomitant Medications:

START DATE	STOP DATE	ACTION
Known	Known	If stop date < study med start date, assign as prior If stop date >= study med start date and start date <= end of treatment, assign as concomitant If stop date >= study med start date and start date > end of treatment, assign as post study
	Partial	Impute stop date as latest possible date (i.e. last day of month if day unknown or 31 st December if day and month are unknown), then: If stop date < study med start date, assign as prior If stop date >= study med start date and start date <= end of treatment, assign as concomitant If stop date >= study med start date and start date > end of treatment, assign as post treatment
	Missing	If stop date is missing could never be assumed a prior medication If start date <= end of treatment, assign as concomitant If start date > end of treatment, assign as post treatment
Partial	Known	Impute start date as earliest possible date (i.e. first day of month if day unknown or 1 st January if day and month are unknown), then: If stop date < study med start date, assign as prior If stop date >= study med start date and start date <= end of treatment, assign as concomitant If stop date >= study med start date and start date > end of treatment, assign as post treatment
	Partial	Impute start date as earliest possible date (i.e. first day of month if day unknown or 1 st January if day and month are unknown) and impute stop date as latest possible date (i.e. last day of month if day unknown or 31 st December if day and month are unknown), then: If stop date < study med start date, assign as prior If stop date >= study med start date and start date <= end of treatment, assign as concomitant If stop date >= study med start date and start date > end of treatment, assign as post treatment

Statistical Analysis Plan

START DATE	STOP DATE	ACTION
	Missing	Impute start date as earliest possible date (i.e. first day of month if day unknown or 1 st January if day and month are unknown), then: If stop date is missing could never be assumed a prior medication If start date <= end of treatment, assign as concomitant If start date > end of treatment, assign as post treatment
Missing	Known	If stop date < study med start date, assign as prior If stop date >= study med start date, assign as concomitant Cannot be assigned as 'post treatment'
	Partial	Impute stop date as latest possible date (i.e. last day of month if day unknown or 31 st December if day and month are unknown), then: If stop date < study med start date, assign as prior If stop date >= study med start date, assign as concomitant Cannot be assigned as 'post treatment'
	Missing	Assign as concomitant

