6.2. BASELINE

Unless otherwise specified, baseline is defined as the last non-missing measurement taken on or prior to reference start date (including unscheduled assessments). In the case where the last non-missing measurement and the reference start date coincide, that measurement will be considered pre-baseline, but Adverse Events (AEs) and medications commencing on the reference start date will be considered post-baseline.

Baseline for calculated LDL-C, HDL-C, non-HDL-C, TG, and TC is defined as the mean of the values from Week -1 (Visit S3) and predose Day 1/Week 0 (Visit T1) (i.e., the last two non-missing values on or prior to Day 1). If only one value is available then that single value will be used as baseline.

Baseline for apoB and hsCRP is defined as the predose Day 1/Week 0 (Visit T1) value (i.e. the last non-

[REDACTED]
[REDACTED]

Statistical Analysis Plan

missing value on or prior to Day 1). If this is not available, then the last non-missing value prior to the first dose of double-blind study medication (including unscheduled assessments) will be used as baseline.

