18.1. ADVERSE EVENTS

Adverse Events (AEs) will be coded using MedDRA, Version 20.1.

Treatment emergent adverse events (TEAEs) are defined as AEs that started or worsened in severity after the first dose of double-blind study medication and prior to the last date of study medication + 30 days. AEs that occurred on day 1 will be only be determined as TEAE if the site indicated it occurred after first dose on the AE CRF.

See [Appendix 2](#) for handling of partial dates for AEs. In the case where it is not possible to define an AE as treatment emergent or not, the AE will be classified by the worst case scenario, i.e. treatment emergent.

An overall summary of number of patients within each of the categories described in the sub-section below, will be provided as specified in the templates. Listings will include TEAEs and Non-TEAEs.

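### SAP Appendix 2 applies the last dose + 30 day limit to the stop date when the AE start date is partial or missing, and its Day 1 rule conflicts with SAP 18.1, so some TEAE flags are undefined or contradictory

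*SAP*

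**What the plan says.** SAP 18.1 (Adverse Events) sets the window by onset or worsening: "after the first dose of double-blind study medication and prior to the last date of study medication + 30 days". It adds a Day 1 condition: "AEs that occurred on day 1 will be only be determined as TEAE if the site indicated it occurred after first dose". It refers to Appendix 2 for partial dates, and says that where emergence cannot be decided, "the AE will be classified by the worst case scenario, i.e. treatment emergent".

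SAP Appendix 2 (Partial Date Conventions) turns this into a table. The three known-start rows test the start date against first dose and against last dose + 30 days. The row for partial starts that must precede first dose gives not TEAE. For the remaining partial starts, and for missing starts, the outcome depends on the stop date:

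- Stop before first dose: not TEAE.
- Stop known, or partial and imputed to its latest possible date: "If stop date >= study med start date and <=study med end date + 30, then TEAE".
- Stop missing: presumed TEAE.

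The known-start rows count any start on or after the first-dose date. They carry no Day 1 condition.

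**The concern.** Treatment emergence is a property of onset. Once an event began on drug, the date it resolved should not affect its classification. In the partial-start and missing-start rows it does: the same event can be a TEAE if its start day was recorded, have no outcome if only that day is missing, and be a TEAE again if it never resolved. The Day 1 conflict is a separate matter. Two parts of one SAP give different answers for a fully dated event.

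TEAE incidence is the first safety endpoint in Protocol 5.2.4, and the flag feeds the overall, serious, related, discontinuation and special-interest tables, including those listed for the DMC in SAP Appendix 3. Two programmers following the same SAP could produce different counts.

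**Working it through.** The plan gives no figure to reproduce, so the check applies the Appendix 2 table literally to illustrative dates and compares the result with the 18.1 definition.

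Assumed dates: first dose 1 Jun 2017; last dose 1 Oct 2017 (a patient who stopped study drug early and stayed in follow-up). Window end = 1 Oct + 30 days = 31 Oct 2017.

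| AE start | AE stop | Appendix 2 | SAP 18.1 |
|---|---|---|---|
| 15 Aug 2017 | 15 Dec 2017 | TEAE | TEAE |
| Aug 2017, day missing | 15 Oct 2017 | TEAE | TEAE |
| Aug 2017, day missing | 15 Dec 2017 | no outcome | TEAE |
| Aug 2017, day missing | 2017, imputed to 31 Dec | no outcome | TEAE |
| Aug 2017, day missing | missing | TEAE | TEAE |
| missing | 15 Dec 2017 | no outcome | TEAE, by the worst-case sentence |
| Dec 2017, day missing | missing | TEAE | not TEAE |
| 1 Jun 2017 (Day 1), before dosing | 3 Jun 2017 | TEAE | not TEAE |

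**Late stops.** In rows 3 and 4 every possible August onset lies between first and last dose, so the missing day is immaterial under 18.1. The table still returns nothing, because the stop is after 31 Oct. Imputing a partial stop to its latest date makes this more likely.

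**Late onsets.** In row 7 the earliest possible onset is 1 Dec 2017, 61 days after last dose and outside the window. The missing stop nevertheless makes it a TEAE.

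**Day 1.** In row 8 the start is fully known, so partial-date handling is not involved. The two sections simply disagree.

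**Can such events arise?** Yes. Protocol 10.3.1 asks patients who stop study drug to remain on the visit schedule, 11.2.3 collects AEs to study completion or discontinuation, and 11.2.6 follows ongoing AEs for up to 30 days after the last visit. Stops later than last dose + 30 days can therefore be recorded, mainly in early stoppers.

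**Comparison within the appendix.** The medication algorithm in Appendix 2 imputes a partial start to its earliest date and tests that start against end of treatment. With a missing start, any stop on or after first dose makes the medication concomitant, with no upper limit on the stop. The AE rows depart from this without explanation.

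**Size.** The documents give no AE counts. Assume about 2,000 AEs, 1% to 3% of them with a partial or missing start, and 10% of those stopping after last dose + 30 days:

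- 2,000 × 0.01 × 0.10 = 2 events
- 2,000 × 0.03 × 0.10 = 6 events

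These are events left without an outcome by the table. No inputs are available to size the late-onset or Day 1 parts.

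**The case against.** The strongest reply is that for late stops the table does not say not TEAE; it says nothing, and the worst-case sentence in 18.1 exists for events that cannot be classified. Read together, the two sections can make these events TEAEs. That stands. A reader might infer that the plan drops long-lasting events, or always under-counts; the documents do not support either. Whether the flag is lost depends on how the gap is coded, unresolved events are presumed TEAEs, the test is on stop date relative to last dose and not on duration, and the Day 1 rule errs towards over-flagging. The listings also include non-TEAEs.

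The reply does not close the gap. In the known-start rows, a start after the window also falls through without an outcome, and there 18.1 plainly means not TEAE. A programmer who treats falling through as not TEAE in those rows may well do the same in the stop-date rows.

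Two further inferences should be resisted. The row reading "If stop date < study med start date and <=study med end date + 30, then not TEAE" looks like an error that changes results. It does not, because a stop before first dose always precedes last dose + 30 days, so the second condition is redundant. And SAP 6.2, which says "Adverse Events (AEs) and medications commencing on the reference start date will be considered post-baseline", is not a third TEAE definition: it separates baseline from post-baseline and does not mention treatment emergence.

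It is also fair that Protocol 11.2.3 requires an onset date and 16.3 forbids blank fields, which should keep partial starts uncommon, and that SAP 18 plans no between-group safety tests unless specified.

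**Conclusion.** The point holds in limited form. For partial starts that could be on or after first dose, and for missing starts, Appendix 2 tests the wrong date against the + 30 day limit. It gives no outcome for late stops and presumes a TEAE for some onsets that 18.1 excludes. Separately, its known-start rows conflict with 18.1 on Day 1 events. Known starts are otherwise tested on the correct date.

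The effect is small: 2 to 6 events without an assigned outcome, on wholly assumed inputs. Direction differs by part: possible under-counting for late stops if the gap is coded as not TEAE, and over-counting for late onsets with a missing stop and for pre-dose Day 1 events. No efficacy result is touched. It is worth correcting because the flag underlies most safety tables and the correction is cheap.

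**What to change.** In Appendix 2, replace the stop-date rows for partial and missing starts with one rule. Classify as not TEAE only if (a) the stop date, imputed to its latest possible date when partial, is before first dose, or (b) the known start components place onset before first dose or after the last dose + 30 day window. Otherwise classify as TEAE.

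Copy the existing 18.1 Day 1 condition into the known-start rows. Reversing the default, so that unmarked Day 1 events count as TEAEs, would change 18.1 and not reconcile the two sections. While editing, align the upper boundary: 18.1 has "prior to the last date of study medication + 30 days", whereas Appendix 2 includes day + 30 itself. The redundant condition can be deleted as tidying.

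The cost is a few table rows and a small change to the flag derivation. Because the SAP addendum reports that the planned analysis is complete, the sponsor should also confirm which rule was coded and list any AE whose flag changes.

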APPENDIX 3. LIST OF DMC TABLES, LISTINGS, AND FIGURES

TABLES

- 14.1.1.1 Patient Disposition – All Patients
- 14.1.2.1a Demographic and Other Baseline Characteristics – Full Analysis Set
- 14.1.3.1 Medical/Surgical History – Full Analysis Set
- 14.1.3.3 Targeted Cardiovascular History/Risk Factors – Full Analysis Set
- 14.1.5.1 Study Drug Compliance – Safety Analysis Set
- 14.3.1.1 Overview of Treatment-Emergent Adverse Events – Safety Analysis Set
- 14.3.1.2 Treatment-Emergent Adverse Events by Maximum Severity, System Organ Class and Preferred Term – Safety Analysis Set
- 14.3.1.3 Serious Treatment-Emergent Adverse Events by Maximum Severity, System Organ Class and Preferred Term – Safety Analysis Set
- 14.3.1.4 Related Treatment-Emergent Adverse Events by Maximum Severity, System Organ Class and Preferred Term – Safety Analysis Set
- 14.3.1.5 Related Serious Treatment-Emergent Adverse Events by Maximum Severity, System Organ Class and Preferred Term – Safety Analysis Set
- 14.3.1.6 Treatment-Emergent Adverse Events That Led to Discontinuation of Study Drug by Maximum Severity, System Organ Class and Preferred Term – Safety Analysis Set
- 14.3.1.8 Treatment-Emergent AESIs by Maximum Severity, System Organ Class and Preferred Term – Safety Analysis Set
- 14.3.1.15 Investigator-reported Major Cardiac Events (MACE) by Event Type – Safety Analysis Set
- 14.3.1.16 Adjudicated Major Cardiac Events (MACE) by Event Type – Safety Analysis Set
- 14.3.2.8 Laboratory Parameters of Interest: Observed and Change from Baseline – Safety Analysis Set
- 14.3.2.9 Laboratory Parameters of Interest: Laboratory Abnormalities – Safety Analysis Set

Statistical Analysis Plan

14.3.2.10 Quantitative Clinical Laboratory Evaluations: Lipids – Safety Analysis Set (note that this table is produced for DMC only)

FIGURES

14.3.1 Boxplots of Hematology Parameters

14.3.2 Boxplots of Chemistry Parameters

The next 2 listings will be created at the same time frame as DMC TLFs above. However, these 2 listings will be sent to Esperion Team only for monitoring thresholds for protocol deviations and for evaluable patients, but not sent to DMC members.

Listing 16.2.3 Patient Inclusion per Analysis Population – All Screened Patients

Listing 16.2.4 Screen Failures – All Screened Patients (note that this listing is produced for DMC only)

APPENDIX 4. DETAILS OF MULTIPLE IMPUTATION METHOD

Missing Week 12 values will be imputed based on baseline values. The following table details the possible cohorts and which cohorts will be used for imputation. Missing Week 24 values will be imputed in the same way.

	Treatment	Week 12 Value	On Treatment at Week 12	Imputation Cohort(s)
1	Placebo	Missing	Yes	Cohort 5: Placebo patients with non-missing Week 12
2	BA	Missing	Yes	Cohorts 6 and 8 BA patients with non-missing Week 12
3	placebo	Missing	No	Cohort 5: Placebo patients with non-missing Week 12
4	BA	Missing	No	Cohorts 5 and 7 Placebo patients with non-missing Week 12 and not on treatment
5	placebo	Non-missing	Yes	
6	BA	Non-missing	Yes	
7	placebo	Non-missing	No	
8	BA	Non-missing	No	

Imputation code for Cohorts 1-3.

```
proc mi;
where cohort in(1,2,3,5,6,8);
class trt01pn strata;
monotone regression;
var trt01pn strata base aval;
run;
```

Imputation code for Cohort 4.

```
proc mi;
where cohort in(4,5,7);
class strata;
monotone regression;
var strata base aval;
run;
```

Statistical Analysis Plan

Two hundred imputed datasets will be created, with results from the analysis of each imputed dataset (ANCOVA) combined using Rubin's method.

[REDACTED]

[REDACTED]

[REDACTED]

[REDACTED]

Version Number:
Version Date:

0.5
14June2018

Statistical Analysis Plan

Adverse Event Terms per Protocol	Associated MedDRA Preferred Terms
	increased
Renal disorders	Creatinine renal clearance abnormal
Renal disorders	Creatinine renal clearance decreased
Renal disorders	Glomerular filtration rate abnormal
Renal disorders	Glomerular filtration rate decreased
Renal disorders	Oliguria
Renal disorders	Prerenal failure
Renal disorders	Renal failure
Renal disorders	Renal function test abnormal
Renal disorders	Renal impairment
Gout	Gout

[REDACTED]

[REDACTED]

[REDACTED]

[REDACTED]

Addendum to Statistical Analysis Plan

Title: A LONG-TERM, RANDOMIZED, DOUBLE-BLIND, PLACEBO-CONTROLLED, MULTICENTER STUDY TO EVALUATE THE EFFICACY OF BEMPEDOIC ACID (ETC-1002) IN PATIENTS WITH HYPERLIPIDEMIA AT HIGH CARDIOVASCULAR RISK NOT ADEQUATELY CONTROLLED BY THEIR LIPID-MODIFYING THERAPYE

Protocol: ETC-1002-047

Clinical Phase: 3

Product: ETC-1002

Date: Dec 17, 2018

Addendum to the Statistical Analysis Plan for Study 1002-047

Post-hoc Analyses

Esperion completed the planned analysis as described in Study 1002-047 SAP for all data collected in the study. After unblinding, additional tables and figures were generated to address some issues of clinical interest.

The tables and figures may be presented in the manuscript, presented in the top line results press release, reported in the CSR, and included the communications with the regulatory agencies for the NDA/MAA submissions.

The listing of tables and figures for the post-hoc analyses is provided in the table below.

Table 17.2.4.1a	Efficacy Subgroup Analysis: Percent Change from Baseline to Week 12 in Low Density Lipoprotein Cholesterol (LDL-C) by Derived Baseline Statin Intensity / Full Analysis Set
Table 17.2.4.1b	Efficacy Subgroup Analysis: Percent Change from Baseline to Week 12 in Low Density Lipoprotein Cholesterol (LDL-C) by Baseline Lipid-modifying / Therapies (LMT) Medications Full Analysis Set
Table 17.2.2.6a	Key Secondary Efficacy Non-parametric Analysis: Wilcoxon Rank Sum Test on Percent Change from Baseline to Week 12 and 52 in High-Sensitivity C-reactive Protein (hsCRP) by Derived Baseline Statin Intensity / Full Analysis Set
Table 17.2.2.6b	Key Secondary Efficacy Non-parametric Analysis: Wilcoxon Rank Sum Test on Percent Change from Baseline to Week 12 and 52 in High-Sensitivity C-reactive Protein (hsCRP) by Baseline Lipid-modifying Therapies (LMT) Medications / Full Analysis Set
Table 17.2.2.6c	Key Secondary Efficacy Non-parametric Analysis: Wilcoxon Rank Sum Test on Percent Change from Baseline to Week 24 and 52 in High-Sensitivity C-reactive Protein (hsCRP) On-Treatment Analysis / Full Analysis Set
Table 17.3.1.1	Incidence of Positively Adjudicated Treatment-Emergent Composite Clinical Endpoints / Safety Analysis Set
Table 17.4.1.1	Post-Randomization Abnormal Liver Function Summary / Safety Analysis Set
Figure 19.1.1	Waterfall Plot of Percent Change from Baseline to Week 12 in Low Density Lipoprotein Cholesterol (LDL-C) / Full Analysis Set
